3.2.1.1 Primary efficacy analysis

The ORR defined as the proportion of subjects with a best overall response (BOR) of a partial response (PR) or complete response (CR) as assessed by independent central review will be estimated in Cohort A tested versus the threshold of 10% using a one-sample exact test for binomial distribution. A higher response rate over 10% will be considered statistically significant if the p-value for the one-sided test is less than 0.025. The statistical testing will only be carried out at the final analysis.

The ORR estimates will be presented in statistical tables with their associated 2-sided 95% CIs using Clopper-Pearson exact method (Tables 14.2.1.1 based on Efficacy population and 14.2.1.2 based on Per Protocol population).

The SAS code below will be used:

```
proc freq data=<dataset>;
  [by <cohort>];
  tables <response> / binomial (level='1' p=0.10) alpha=0.05;
  exact binomial;
run;
```

3.2.1.2 Secondary efficacy analysis

The secondary efficacy endpoints will be analysed as below.

- (a) Time-to-event endpoints such as TTR (Table 14.2.1.3 and 14.2.1.4, and Figure 14.2.1.5) will be analysed using the Kaplan-Meier method. The results will be presented for each Cohort A and B both in summary tables and graphically in Kaplan-Meier plots. Kaplan-Meier methodology will be used to characterise the distribution of endpoints. Median durations and associated 2-sided 95% CIs will be provided, as well as 25th and 75th percentiles. Event rates at timepoints will also be estimated with associated 2-sided 95% CIs.
- (b) DOR will be analysed using the Kaplan-Meier method (Tables 14.2.1.3 and 14.2.1.4, and Figure 14.2.1.6).
- (c) DCR estimates will be presented in statistical tables with associated 2-sided 95% CIs (Tables 14.2.1.3 and 14.2.1.4).
- (d) PFS will be analysed using the Kaplan-Meier method (Tables 14.2.2.1 and 14.2.2.2, and Figure 14.2.2.3).
- (e) OS will also be analysed using the Kaplan-Meier method (Tables 14.2.3.1 and 14.2.3.2, and Figure 14.2.3.3).
- (f) The ORR according to Investigator's assessment (cohort A and cohort B) and by independent central review (cohort B) will be presented with their associated 2-sided 95% CIs using Clopper-Pearson exact method (Table 14.2.4.1). TTR, DOR, DCR and PFS according to Investigator's assessment will be analysed in the same way as these endpoints assessed by independent central review (Tables 14.2.4.5 and 14.2.4.6, Figures 14.2.4.8 and 14.2.4.9, Tables 14.2.5.1 and 14.2.5.2, and Figures 14.2.5.3 and 14.2.5.4).
- (g) For the 9-item subset of disease related symptoms of the FSKI-DRS, the total score will be calculated using the number of subjects having a Baseline

SAP Final: Version 6.0: 17 August 2023

and at least one post-Baseline completion score. Baseline will be defined as the last questionnaire answered prior to the first dose of study drug. Subject will rate each question from 0 to 4. Total score will be calculated as the sum of the item responses divided by the number of items completed and multiplied by the total number of items in the scale. Completion score will be defined as answering at least 5 of 9 items i.e. total score will be derived only if at least 5 items were answered. Total score ranges will be from 0 to 36 (see [Appendix 1 \(6\)](#)). Descriptive statistics will be performed at each timepoint and change from Baseline (Tables 14.2.6.1 and 14.2.6.2). Comparisons between Baseline and post-Baseline scores will be performed using paired Student t-tests. The proportion of subjects with at least one increase of 1 point, 3 points and 5 points from Baseline will also be reported. The graph of change from Baseline over time will be presented (Figure 14.2.6.3).

Change from baseline in tumour size over time will be summarized (Tables 14.2.1.7 and 14.2.1.8 for independent review, and Tables 14.2.4.10 and 14.2.4.11 for investigator assessments). The tumour size will be the sum of diameters of target lesions measured by independent review, or by investigators. The change from baseline will be calculated as defined in [Appendix 1 \(7\)](#), and the percent change from baseline as defined in [Appendix 1 \(8\)](#). The best percentage change from baseline (biggest decrease, or smallest increase if no decrease) will be presented by waterfall plots (Figure 14.2.1.9 for independent review, and Figure 14.2.4.12 for investigator assessments). The nadir and percent change from nadir will be calculated as defined in [Appendix 1 \(9\)](#) and listed.

The ORR will also be presented by subgroup defined in Section [3.2.16](#) (Tables 14.2.1.10 and 14.2.1.11 for independent review, and Tables 14.2.4.13 and 14.2.4.14 for investigator assessments).

ORR and tumour response (TTR, DoR and DCR) will also be presented for both independent central review and investigator assessments (Tables 14.2.4.2 and 14.2.4.7). The results are available but on different tables (Tables 14.2.1.1 and 14.2.4.1, and Tables 14.2.1.3 and 14.2.4.5, respectively), this is only a different presentation.

Concordance in Overall Response Rate and BOR assessed by independent central review and by Investigator will be described using shift tables for each cohort separately (Tables 14.2.4.3 and 14.2.4.4). The concordance will be presented for the subjects with assessments in both populations i.e. from both IRC and investigator assessments.

General censoring rules for the analysis of PFS are described in [Appendix 1 \(4\)](#).

Additional supportive analyses of PFS below will be performed using alternative event definitions and censoring schemes to account for partial or completely missing assessments, address bias due to tumour assessment timing, evaluate the impact of potentially informative censoring, and to address potential discrepancies between the

SAP Final: Version 6.0: 17 August 2023

documentation of progression per the Investigator and per the independent central review. This is applicable for PFS only. These additional supportive analyses will be performed on the Efficacy population only.

- The primary PFS analyses described above will be repeated with the same general censoring rules, except that the progression or death will be considered a PFS event regardless of when it occurs during the study i.e. the event will be considered a PFS event even if the subjects missed two or more scheduled tumour assessment prior this event and/or even if the subjects received NPACT prior the event (Table 14.2.2.4, Figure 14.2.2.5, Table 14.2.5.5 and Figure 14.2.5.6);
- The primary PFS analyses described above will be repeated with the same general censoring rules, except that non-radiological disease progression will also be considered a PFS event (Table 14.2.2.6, Figure 14.2.2.7, Table 14.2.5.7 and Figure 14.2.5.8).
- The primary PFS analyses described above will be repeated with the same general censoring rules, with additional censoring at last tumour assessment prior to treatment discontinuation for subjects who discontinued study treatment due to reasons other than PD or death (Table 14.2.2.8, Figure 14.2.2.9, Table 14.2.5.9 and Figure 14.2.5.10).

3.2.2 *Safety*

All safety data will be included in the subject data listings. Analyses and summary tables will be based upon the safety population as defined in Section 2.2 and will be presented in each cohort separately and overall.

3.2.2.1 *Adverse events*

All AEs will be coded according to the most recent version of the Medical Dictionary for Regulatory Activities (MedDRA) and will be classified by PT and SOC. AEs will be graded according to the NCI-CTCAE version 5.0.

Adverse event listings (Listings 16.2.7.1 to 16.2.7.9) will be presented by cohort, subject id, SOC and PT. Listings of serious adverse events (SAEs), adverse events leading to withdrawal and listings of deaths will also be presented. Treatment-emergent AEs (TEAEs) will be flagged (*) in the AEs listings and will be summarized.

A TEAE is defined as any AE that occurs after first dose of study drug if:

- it was not present prior to receiving the first dose of study drug, or
- it was present prior to receiving the first dose of study drug but the intensity increased during the active phase of the study.

The focus of analysis for this study will be the duration of the treatment period and 30 days after the date of last study drug administration.

If AE start and/or stop dates are missing or partial, the rules mentioned in Section 3.2.3.2 will be applied, and the algorithm for imputation is defined in Appendix 1 (10).

SAP Final: Version 6.0: 17 August 2023

A summary table of overall counts will include the number of subjects with: any AE, any TEAE, any TEAE of Grade 3 or 4, any study drug related TEAE, any study drug related TEAE of Grade 3 or 4, any serious TEAE, any study drug related serious TEAE, any TEAE leading to study drug withdrawal, any TEAE leading to study drug interruption, any TEAE leading to a dose reduced, any TEAE leading to death (Table 14.3.1.1). TEAEs associated with change of schedule of administration will be defined as those with an action taken with study drug as dose reduced or study drug interrupted.

The incidence of all TEAEs will be tabulated by cohort and overall, with the number and percentage of subjects with adverse events classified by SOC (ordered alphabetically) and PT (in descending order of overall PT incidence) (Table 14.3.1.2). The number of occurrences of a TEAE will also be presented. Summary of TEAEs with incidence rate above or equal 10% will also be presented (Table 14.3.1.3).

In addition, summary tables will be presented for TEAEs of Grade 3 or 4 (Table 14.3.1.4), by worst reported severity (Table 14.3.1.7), by investigator causality (Table 14.3.1.8), for related TEAEs of Grade 3 or 4 (Table 14.3.1.9), by decreasing frequency (Tables 14.3.1.10 and 14.3.1.11), for TEAEs related to Laboratory Tests (Table 14.3.1.12), and for non-serious TEAEs with incidence rate above or equal 5% (Table 14.3.1.13).

The incidence of all SAEs will also be tabulated with similar presentation (Table 14.3.2.1).

In addition, summary tables will be presented for SAEs with incidence rate above or equal 5% (Table 14.3.2.2), related SAEs (Table 14.3.2.3), TEAEs associated with premature study drug withdrawal (Table 14.3.2.4), related TEAEs associated with premature study drug withdrawal (Table 14.3.2.7), TEAEs associated with study drug interruption (Table 14.3.2.8), related TEAEs associated with study drug interruption (Table 14.3.2.9), TEAEs associated with dose reduction of study medication (Table 14.3.2.10), related TEAEs associated with dose reduction of study medication (Table 14.3.2.11), and suspected or confirmed COVID-19 (SARS-CoV-2) infection TEAEs (Table 14.3.2.12).

In the event of multiple occurrences of the same adverse events being reported by the same subject, the maximum intensity grade (Grade 5 > Grade 4 > Grade 3 > Grade 2 > Grade 1 > missing > not applicable) and the most serious causality (related > not related) will be chosen and used in the summaries. So, the adverse event will be counted only once with the worst intensity and worst causality. If causality is missing, the worst case will be assumed.

Time-to-event plots will also be presented using the Kaplan-Meier method for time from first study dose to any TEAE of Grade 3 or 4 (Table 14.3.1.5 and Figure 14.3.1.6), and time to any TEAE leading to drug withdrawal (Table 14.3.2.5 and Figure 14.3.2.6).

The time from first dose will be calculated as defined in [Appendix 1 \(11\)](#).

SAP Final: Version 6.0: 17 August 2023

Summary tables of related SAEs reported in post-treatment follow-up period (i.e. starting more than 30 days after the date of the last cabozantinib dose) will also be presented (Table 14.3.2.13). During the Post-treatment Follow-up period, only SAEs assessed as related to cabozantinib or study procedures, will be collected.

Summary tables of TEAEs leading to death, and of AEs occurring during post-treatment follow-up period and leading to death, will also be presented (Table 14.3.2.14 and 14.3.2.15), as well as by causality (Table 14.3.2.16 and 14.3.2.17). AEs leading to death are AEs with an outcome of death and/or an NCI-CTCAE Grade 5. All subject deaths reported on the death form will be summarised (Table 14.3.2.18). Subject deaths under treatment with study drug (i.e. deaths until 30 days after the date of the last cabozantinib dose) and after treatment with study drug will also be presented separately (Tables 14.3.2.19 and 14.3.2.20).

The incidence of Adverse Events of Special Interest (AESI)/Events to Monitor (ETM) will be tabulated by cohort and overall, with the number and percentage of subjects with adverse events classified by type of event (ordered alphabetically) and PT (in descending order of overall PT incidence) (Table 14.3.2.21). A summary table will be presented for AESIs of Grade 3-4, Grade 4 and Grade 5 (Table 14.3.2.22).

The list of AESI/ETM will be as below:

- Gastrointestinal perforation
- Gastrointestinal and non-gastrointestinal fistula
- Thromboembolic events
- Haemorrhage (Grade ≥ 3)
- Wound complications
- Posterior reversible encephalopathy syndrome (PRES)
- Osteonecrosis
- Renal failure
- Hepatotoxicity
- Embryotoxicity
- Carcinogenicity.

3.2.2.2 *Laboratory data*

Laboratory data (haematology, coagulation, thyroid function, blood chemistry and urinalysis) will be listed in standard international (SI) units (Listings 16.2.8.1.1 to 16.2.8.1.7). Any unscheduled laboratory assessments will be flagged in the listings. A list of clinically significant abnormal values will be presented (Listing 16.2.8.1.8). This listing will present all laboratory values of the laboratory parameter for a subject with at least one clinically significant abnormal value for a laboratory parameter. The abnormality will be as per reported in eCRF.

SAP Final: Version 6.0: 17 August 2023

For all laboratory parameters, the Baseline will be defined as the last measurement collected prior to the first dose of study drug.

As more than one laboratory will be involved in the study for the measurement of laboratory values, a normalisation method will be required in order to take into account the multiple reference ranges [3] for haematology, biochemistry, and urinalysis parameters. The site which has analysed the largest number of blood samples will be used as the reference site. The following formula will be used:

$$\text{Normalised value} = L_R + (x - L_X) \frac{U_R - L_R}{U_X - L_X}$$

With LR the reference site lower limit, UR the reference site upper limit, LX the local site lower limit, UX the local site upper limit and x the non normalised value assessed in the local laboratory. Reference site lower/upper limits, local site lower/upper limits and local value are converted in the SI unit.

If a normalised value is negative it will be replaced by 0.

The neutrophils values will be imputed as defined in [Appendix 1 \(12\)](#).

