For the 9-item subset of disease related symptoms of the FCSI-DRS, the total score will be calculated using the number of subjects having a baseline and at least one post-baseline completion score. Completion score will be defined as answering at least 5 of 9 items. Descriptive statistics will be performed at each timepoint and change from baseline. Comparisons between baseline and post-baseline scores will be performed using paired Student t-tests. The proportion of subjects with at least an increase of 1 point from baseline will also be reported.

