| 38 | Appendix 1 | 08Aug2019 | 06Oct2021 | 
Reordered and renumbered to follow the core SAP order.
 
Updated the derivation for the TTR, DoR, PFS and OS.
 
Added the derivation for FKSI-DRS Total Score to provide clarifications.
 
Corrected the formula for the Percent reduction from Baseline.
 
Removed the AE duration.
 
Added the time from first study dose for AE.
 
Removed the time since last dose for AE.
 
Added urinalysis derivation.
 
Updated the derivation for NCI-CTC AE grades.
 
Updated the derivation for Study exposure to consider the Informed Consent and not the Screening as starting point.
 
Updated the derivations for Study drug exposure and Compliance due to CRF update.
 
Added the treatment duration on 1st anti-cancer therapy.
 
Removed Concomitant therapy duration.
 
Updated the derivation for Study day.
 |
| 41 | Appendix 2 | 08Aug2019 | 06Oct2021 | Updated the List of Tables, Figures and Listings due to updates in the Core SAP. |
| 16 | List of Abbreviations | 06Oct2021 | 28Jun2022 | Deleted MET (Hepatocyte Growth Factor Receptor Protein) and PD-L1 (Programmed Death-ligand 1 protein) |

CONFIDENTIAL

SAP Final: Version 6.0: 17 August 2023

| History of Changes | | | | |
|--------------------|---------|------------------|------------------|---|
| Old Version Number | | Date Old Version | Date New Version | Reason for Change |
| Page | Section | Was | Is | |
| 19 | 1.1.1 | 06Oct2021 | 28Jun2022 | Added in cohort A to remove cohort B from the primary objective following protocol amendment #4. |
| 19 | 1.1.2 | 06Oct2021 | 28Jun2022 | Added ORR evaluated by independent central review in cohort B following protocol amendment #4. Added Investigator review of ORR and PFS and added OS assessment for cohorts A and B following protocol amendment #4. |
| 19 | 1.2 | 06Oct2021 | 28Jun2022 | Updated the number of subjects in study design following protocol amendment #4. |
| 21 | 1.2.1 | 06Oct2021 | 28Jun2022 | Updated the study population to stick to protocol Section 1.6. Updated the number of subjects to be included following protocol amendment #4. |
| 21 | 1.2.2 | 06Oct2021 | 28Jun2022 | Updated study exposure period following protocol amendment #4. |
| 21 | 1.3.1 | 06Oct2021 | 28Jun2022 | Updated from anonymise to pseudonymise |
| 27 | 1.3.3 | 06Oct2021 | 28Jun2022 | Updated the schedule of assessments to delete the tumour assessments following protocol amendment #4. |

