- Chronic co-administration of cabozantinib with strong inducers of the cytochrome P450 Family 3 Subfamily A Member 4 (CYP3A4) family (e.g. dexamethasone, phenytoin, carbamazepine, rifampin, rifabutin, rifapentine, phenobarbital, and St. John's Wort) may significantly decrease cabozantinib concentrations and should be avoided. Selection of alternate concomitant medications with no or minimal CYP3A4 enzyme induction potential is recommended;
- Caution must be used when discontinuing study treatment with a strong CYP3A4 inducer in a subject who has been concurrently receiving a stable dose of cabozantinib, as this could significantly increase the exposure to cabozantinib;
- Co-administration of cabozantinib with strong inhibitors of the CYP3A4 family (e.g. ketoconazole, itraconazole, clarithromycin, indinavir, nefazodone, nelfinavir, and ritonavir) may increase cabozantinib concentrations and should be avoided. Grapefruit and Seville oranges may also increase plasma concentrations of cabozantinib and should be avoided.

3.2.11 *Derived data*

Derived data are detailed in [Appendix 1: Derived Data](#).

3.2.12 *Visit windows*

All data will be organised and analysed according to the scheduled visits outlined in the protocol. However, actual observation times may differ from the scheduled visit times and where this occurs the results should be allocated to the most appropriate visit. Therefore, time intervals (e.g. visit windows) have been constructed so that every observation collected can be allocated to a particular time point. If more than one record occurs within the same visit window where only one assessment is expected then the following rule should be applied: for pre-study assessments the last non-missing result prior to study drug administration should be used; for post-treatment assessments the first closest non-missing result to the scheduled visit should be used.

Baseline will be defined as the last non-missing result prior to the first dose of study drug. As the time of first dose is not planned to be collected, assessments on the day of first dose will be considered prior to first dose if such procedures are required by

SAP Final: Version 6.0: 17 August 2023

the protocol to be conducted before first dose, except if a protocol deviation states that the assessment was collected after the first dose.

The study day will be calculated as defined in [Appendix 1 \(24\)](#).

For tumour assessment, the following visit mapping will be performed:

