Following the Functional Assessment of Cancer Therapy – Kidney Symptom Index – Disease Related Symptoms (Fksi-DRS) Scoring Guidelines Version 4 [4], the 9 item answers will be coded as: “Not at all” = 0, “A little bit” = 1, “Some-what” = 2, “Quite a bit” = 3, and “Very much” = 4.

When at least 50% of items (i.e. 5 items) were answered in the subject questionnaire, the Fksi-DRS Total Score will be calculated as follows.

First, each item will be reversed by doing 4 minus the answer. Then, these individual reversed items will be summed to obtain a score. In last step, this score will be prorated by multiplying by the total number of items in the subscale (i.e. 9) and by dividing by the number of items answered in the questionnaire. This will produce the symptom index score.

The score ranges from a minimum possible score of 0 to a maximum possible score of 36.

As with all FACIT questionnaires, a high score is good. Therefore, a score of “0” is a severely symptomatic subject and the highest possible score is an asymptomatic subject.

(7) Changes from Baseline

Changes from Baseline will be calculated as a difference from Baseline (e.g. assessment at the visit – assessment at Baseline).

(8) Percent change from Baseline

Percent change from Baseline will be calculated as a percentage of change from Baseline (e.g. $100*((\text{assessment at the visit} - \text{assessment at Baseline}) / (\text{assessment at Baseline}))$).

(9) Percent change from nadir

Nadir is the smallest sum of measurements at prior timepoints (including baseline). Percent change from nadir will be calculated as a percentage of change from nadir (e.g. $100*((\text{assessment at the visit} - \text{assessment at nadir}) / (\text{assessment at nadir}))$).

(10) Algorithm for TEAE flag

An AE will be classified as a TEAE in case AE start date is between the first dose of study drug and the last study drug administration plus 30 days.

In case of an incomplete AE start date, an AE start date imputation algorithm will be implemented as described in the Table below. Classification of adverse event according to its treatment-emergent status is then performed using the imputed date.

In the following table, all dates are presented using an YYYY-MM-DD format. As an example, suppose first dose of study drug is equal to 2002-08-11 and several AEs have incomplete start dates.

SAP Final: Version 6.0: 17 August 2023

| Description of incomplete AE start date | Imputed numeric date | Example | |

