| Table 14.2.5.5 | Investigator Assessed Progression-Free Survival (PFS) – Different Censoring 1 (Efficacy Population - Investigator) |
| Figure 14.2.5.6 | Kaplan-Meier Plot of Investigator Assessed Progression-Free Survival (PFS) – Different Censoring 1 (Efficacy Population - Investigator) |
| Table 14.2.5.7 | Investigator Assessed Progression-Free Survival (PFS) – Different Censoring 2 (Efficacy Population - Investigator) |

SAP Final: Version 6.0: 17 August 2023

| | |
|------------------|--|
| Figure 14.2.5.8 | Kaplan-Meier Plot of Investigator Assessed Progression-Free Survival (PFS) – Different Censoring 2 (Efficacy Population - Investigator) |
| Table 14.2.5.9 | Investigator Assessed Progression-Free Survival (PFS) – Different Censoring 3 (Efficacy Population - Investigator) |
| Figure 14.2.5.10 | Kaplan-Meier Plot of Investigator Assessed Progression-Free Survival (PFS) – Different Censoring 3 (Efficacy Population - Investigator) |
| Table 14.2.6.1 | Functional Assessment of Cancer Therapy-Kidney Cancer Symptom Index (FKSI-DRS) Questionnaire (Efficacy Population - Investigator) |
| Table 14.2.6.2 | Functional Assessment of Cancer Therapy-Kidney Cancer Symptom Index (FKSI-DRS) Questionnaire (Per Protocol Population - Investigator) |
| Figure 14.2.6.3 | Graph of Change from Baseline in Therapy-Kidney Cancer Symptom Index (FKSI-DRS) Total Score over Time (Efficacy Population - Investigator) |
| Table 14.3.1.1 | Overview of Adverse Events (Safety Population) |
| Table 14.3.1.2 | Summary of Treatment-Emergent Adverse Events by System Organ Class and Preferred Term (Safety Population) |
| Table 14.3.1.3 | Summary of Treatment-Emergent Adverse Events with Incidence Rate $\geq 10\%$ by System Organ Class and Preferred Term (Safety Population) |
| Table 14.3.1.4 | Summary of Treatment-Emergent Adverse Events with CTCAE Severity Grade 3 or 4 by System Organ Class and Preferred Term (Safety Population) |
| Table 14.3.1.5 | Time to onset for Treatment-Emergent Adverse Events with CTCAE Severity Grade 3 or 4 (Safety Population) |
| Figure 14.3.1.6 | Kaplan-Meier Plot of time to onset for Treatment-Emergent Adverse Events with CTCAE Severity Grade 3 or 4 (Safety Population) |
| Table 14.3.1.7 | Summary of Treatment-Emergent Adverse Events by CTCAE Severity Grade and System Organ Class and Preferred Term (Safety Population) |

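### The FKSI-DRS total score in SAP section 3.2.1.2 (g) omits item reversal and is the mirror image (36 minus the score) of the one in SAP Appendix 1 (6)

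*SAP*

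**What the plan says.** SAP section 3.2.1.2 (g) states that each question is rated from 0 to 4 and then gives a full scoring rule: "Total score will be calculated as the sum of the item responses divided by the number of items completed", multiplied by the number of items in the scale. It requires at least 5 of the 9 items, gives a range of 0 to 36, and refers to Appendix 1 (6) directly after the range. It does not mention reversing the items.

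SAP Appendix 1 (6) codes the answers from *Not at all* = 0 to *Very much* = 4 and continues: "First, each item will be reversed by doing 4 minus the answer". The reversed items are summed and prorated to nine items. It calls a score of 0 severely symptomatic and adds that "the highest possible score is an asymptomatic subject".

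Section 3.2.1.2 (g) then plans descriptive statistics, paired t-tests against baseline, a graph of change over time (Figure 14.2.6.3) and a responder summary: "The proportion of subjects with at least one increase of 1 point, 3 points and 5 points from Baseline will also be reported". Protocol section 11.4.3.4 has a related sentence, "The proportion of subjects with at least an increase of 1 point from baseline will also be reported", but no scoring formula and no statement of direction.

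**The concern.** The SAP gives two scoring rules for one named secondary endpoint, and they run in opposite directions. The nine items in Protocol Appendix 6 are all symptom complaints, so a higher raw answer is worse. Without reversal, a high total means many symptoms, which contradicts the appendix.

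If the rule in section 3.2.1.2 (g) were programmed literally, each mean change and the curve in Figure 14.2.6.3 would change sign. The proportions with an increase of 1, 3 or 5 points would then count worsening rather than improvement. Routine checks would not show this, because both rules share the same range and the same minimum number of items.

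There is a smaller wording question in the same text. The SAP speaks of at least one increase, the protocol of at least an increase. The SAP wording can be read as an increase at any visit, the protocol wording as the size of the increase. SAP section 5 (changes from protocol) lists neither this nor the added 3- and 5-point thresholds.

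**Working it through.** **Inputs.** Item answers x from 0 to 4; nine items; k items answered, with k from 5 to 9 (SAP section 3.2.1.2 (g) and Appendix 1 (6)). All items are symptom statements (Protocol Appendix 6).

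**The two scores.**
- Section 3.2.1.2 (g): S = 9 × Σx / k
- Appendix 1 (6): A = 9 × Σ(4 − x) / k

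**The stated range.** Setting every x to 0 and then to 4 gives S = 0 and 36, and A = 36 and 0, for every k from 5 to 9. Both rules reproduce the stated 0 to 36, so the range does not show which is meant.

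**Relation between them.** Σ(4 − x) = 4k − Σx, so A = 9 × (4k − Σx) / k = 36 − S, whatever k is. Exact enumeration of all 1,876 distinct response patterns (order ignored) for k = 5 to 9 gave no exception. The two scores agree only at 18.

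| Answers | S, section 3.2.1.2 (g) | A, Appendix 1 (6) |
|---|---|---|
| All nine *Not at all* | 0 | 36 |
| All nine *A little bit* | 9 | 27 |
| All nine *Very much* | 36 | 0 |

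**Change from baseline.** Since A = 36 − S at each visit, the change in A is minus the change in S, even when k differs between visits.
- Nine items answered, raw sum falling from 7 to 4: S goes 7 to 4 (−3); A goes 29 to 32 (+3).
- Five items answered, raw sum falling from 6 to 3: S goes 9 × 6/5 = 10.8 to 9 × 3/5 = 5.4 (−5.4); A goes 25.2 to 30.6 (+5.4).

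Both subjects improved, and only A shows that as an increase.

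**Effect on the planned summaries.** Changing the sign of every difference changes the sign of the mean and of the t statistic. It leaves the SD and the two-sided p-value as they were. At a single visit, an increase of at least 1, 3 or 5 points in S is a decrease of that size in A, so the proportion describes a different set of subjects. The documents give no means, SDs or correlations between visits, so the size of that difference cannot be stated.

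**Visit basis.** Take a subject whose changes in A at three visits are +3, −1 and −4; the changes in S are −3, +1 and +4. If an increase at any visit counts, this subject meets the 1- and 3-point thresholds under either rule and the 5-point threshold under neither. The any-visit counts are therefore not simple opposites, and whether the proportion is per visit or any-visit needs stating as well as the direction.

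**The case against.** The SAP largely answers the point itself. Section 3.2.1.2 (g) refers to Appendix 1 (6), and section 3.2.11 makes that appendix the home of derivations ("Derived data are detailed in" Appendix 1). The appendix gives a complete derivation, cites the scoring guideline and states the direction. The history of changes for the 06Oct2021 version records "Added the derivation for FKSI-DRS Total Score to provide clarifications". A programmer who follows the reference gets one unambiguous score, and an increase is then plainly an improvement. The difference between the SAP and protocol wording on increases may be loose English, and the visit basis and footnotes may be set out in the table shells, which are not part of these documents.

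Most of this stands, and it keeps the point minor. It does not make the formula in the analysis section correct. The reference follows the range sentence, which fits both rules, and nothing in the SAP says the appendix prevails over a conflicting formula. The wording point would not justify a comment alone; it is worth settling while the sentence is being edited.

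**Conclusion.** The point holds, at low severity. As written, section 3.2.1.2 (g) gives a score exactly equal to 36 minus the one in Appendix 1 (6). By the SAP's own standard, that a high score is good, the analysis-section formula is the one in error. The identity is algebraic and rests on no assumption about the data.

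Any effect on results is conditional on that formula being programmed. In that case the sign of every mean change, the direction of Figure 14.2.6.3 and the meaning of the increase proportions would be reversed. SDs, two-sided paired t-test p-values and the primary response-rate analysis would not change. Nothing in the documents suggests that any table used the uncorrected formula.

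**What to change.** In SAP section 3.2.1.2 (g), replace the formula with: *sum of (4 minus item response) × 9 / number of items answered, per Appendix 1 (6); higher = fewer symptoms*. State there that an increase means improvement, and repeat this in the footnote to Tables 14.2.6.1 and 14.2.6.2 if the shells do not already carry it.

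In the same edit, say whether the proportion with an increase is reported at each visit or counts an increase at any post-baseline visit, and align this with protocol section 11.4.3.4. List the added 3- and 5-point thresholds in SAP section 5.

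The cost is a few sentences and a footnote. No planned analysis changes.
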